5.4.2 Baseline Disease Characteristics

Baseline disease characteristics will be summarized by treatment group and Total for the ITT population for the following:

- Baseline Historical IDH Rate (0,1,2,3,4)
- Dialysis Vintage
- Baseline b2M Level (V1.5)
- Baseline MoCA
- Baseline PHQ-9

5.4.3 Medical History

The number and percent of subjects reporting various medical histories grouped by system organ class (SOC) and preferred terms (PT) using MedDRA dictionary version 23.0 will be tabulated, as collected in the EDC. Subject medical history as well as allergies, surgeries and procedures will be listed.

5.4.4 Serology

Serology, including hepatitis B surface/core antigen (HBsAg), hepatitis C antibody (HCV Ab), and human immunodeficiency virus antibody (HIV Ab, HIV1/HIV-2), will be collected at Visit 1. Serology will not be summarized but will be provided as a listing.

5.4.5 Baseline Efficacy and Safety Assessment

The Baseline efficacy and safety data needed for the CSR will be extracted from corresponding tables described in the corresponding Efficacy Analysis and Safety Analysis section.

5.5 Protocol Deviations

Protocol deviations will be summarized by treatment group and Total with each deviation category broken down into major and minor for the ITT and Safety populations separately.

5.6 Methods for Handling Missing Data

No imputation of missing data will be performed.

5.7 Efficacy Analyses

Efficacy analyses will evaluate the feasibility of conducting expanded studies of AKST1210 in subjects with ESRD-CI who are undergoing HD 3 times per week, and its efficacy. The efficacy analyses will be descriptive only. Except where indicated, efficacy parameters will be summarized using the Evaluable and PP populations. All efficacy data, regardless of population, will be presented in data listings.

5.7.1 Feasibility of all Procedures

Feasibility of all procedures will be determined by the number of assessments that can be completed by the subject, visits that are completed, dialysis sessions that are completed with the longer dialysis time and the number of times the dialysis session becomes unblinded to treatment. A less than 75% completion by subjects would determine the procedure non-feasible calculated by treatment period and study overall. The percentage of subjects who are missing at each procedure will also be summarized.

5.7.2 Tolerability of Column Size, including Subject Compliance with Visit Completion, Procedures, Subject Retention

The number and percentage of subjects will be summarized by column size (AKST1210 S-15, S-25, and S-35), overall AKST1210 and control for the following:

- Subjects entered into each treatment period
- Subjects who de-escalated to a lower column size in treatment period 3 categorized by reason: IDH only, Anemia only, IDH and Anemia. Anemia is defined as having a hemoglobin (Hgb) lab value of < 9g/dL, Subjects who were discontinued due to treatment or HD
- Subjects who completed all the visits

5.7.3 Change in IDH Rate Above Historical IDH Rate for Column Size

The number and percentage of subjects will be summarized by column size (AKST1210 S-15, S-25, and S-35), overall AKST1210 and control for the following:

- Historical IDH Rate (0,1,2,3,4)
- Number of IDH (0,1,2,3,4,5, 6)
- Change in IDH Rate above the Historical IDH Rate (0,1,2, 3)

A listing of IDH Rate, including each subject's historical IDH rate and number of hypotensive events, will be provided.

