4 STUDY DESIGN AND ENDPOINTS

4.1 DESCRIPTION OF THE STUDY DESIGN

This will be a randomized, double-blind study conducted at up to 5 sites in the US. Approximately 26 male and female subjects, \geq 40 years of age on HD with ESRD-CI, will be enrolled. Assuming a drop-out rate of 20%, enrollment at this level will yield approximately 20 evaluable subjects.

During Screening (Visit 1, Day -42 through Day -14), subjects and/or their legally authorized representative (LAR) will provide informed consent, and subjects will undergo screening assessments including provision of demographics and medical history, physical examination, 12-lead ECG, laboratory testing (including pregnancy testing if applicable), as well as tests to assess cognitive function and depression. A blood sample will also be obtained and sent to the site's local laboratory to determine baseline b2M concentration.

If the Visit 1 Screening eligibility criteria are met, subjects will commence the Run-in Period (Visits 1.1-1.6, Day -14 through Day -1). During Run-in, subjects will undergo HD at a reduced flow rate; have safety assessments; complete tests to assess cognitive function, quality of life, quality of sleep, and fatigue; and have blood samples collected for b2M and plasma proteomics. All subjects will have their HD flow rate adjusted to a maximum flow rate of 250 mL/minute, thus necessitating an increase in the overall length of dialysis time to approximately 4 hours.

Subjects who continue to meet eligibility requirements will be randomized at Visit 2 (Day 1) to one of two treatment arms: AKST1210 (the investigational treatment) or control (no column). The AKST1210 column will be connected in series before (upstream of) the HD dialyzer for the duration of each HD session, and an appropriate covering of either the AKST1210 column or control will be in place for blinding purposes. All randomized subjects will continue to undergo dialysis at the adjusted, maximum flow rate of 250 mL/minute at the extended dialysis time, similar to the Run-in Period. The subject, investigator, and outcomes assessor(s) will be blinded as to treatment (i.e., double-blind study).

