7.1.1.2.2 Monitoring Vital Signs

Vital signs monitoring will occur at every visit. Seated/reclined BP will be recorded before each dialysis session, every 30 minutes during dialysis, and at the end of the session. Other vital signs will be captured at the beginning and end of each visit; these include heart rate (beats per minute [bpm]), respiratory rate (breaths per minute), and body temperature. Vital signs will be measured after the subject has been seated/reclined for ~5 minutes.

Subjects will be monitored for IDH (see [Definitions](#)). During Run-in if a subject experiences 3 or more IDH events then they will be excluded from further participation (see [Section 5.2](#)). After randomization, should the number of occurrences of IDH exceed a predetermined threshold based on the subject's Expected IDH Rate, then the subject will be de-escalated to a lower column size or discontinued as appropriate ([Appendix 17.1](#)).

In subjects who experience IDH, the following questions must be asked to assess whether the IDH is accompanied by cognitive impairment (confusion, disorientation):

- What is your name?
- Where are you?
- What is the day of the week?
- What is today's date and what is the month?
- Who is the President?
- Who is the Governor?

Regardless of whether the subject shows signs of cognitive impairment, it is important that the IDH be addressed expeditiously as per standard procedures at the site. These procedures may include changes to the ultrafiltration rate, Trendelenburg position, and administration of saline. Once the IDH has been addressed and the dialysis session has concluded, the same questions should be asked again to assess whether the transient cognitive impairment (if present) resolved with the resolution of the episode of IDH.

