17 APPENDICES

APPENDIX 17.1 ESCALATION, DE-ESCALATION, AND DISCONTINUATION RULES FOR TREATMENT WITH AKST1210 OR CONTROL

The following definitions are relevant to evaluating whether to escalate, de-escalate, or discontinue a subject:

- **Intradialytic hypotension/hypotensive event (IDH):** A decrease in SBP \geq 20 mm Hg or a decrease in MAP \geq 10 mm Hg associated with symptoms that include: abdominal discomfort; yawning; sighing; nausea; vomiting; muscle cramps; restlessness; dizziness or fainting; and anxiety ([K/DOQI Workgroup 2005](#)).
- **Expected IDH Rate:** The expected number of occurrences of IDH per 4-week treatment period used to assess escalation, de-escalation, and discontinuation. Expected IDH is derived from a subject's Historical IDH Rate (see table below).
- **Historical IDH Rate:** The number of occurrences of IDH as documented in a subject's medical record during a recent, consecutive 8-week interval prior to randomization. This 8-week period may include the 2-week Run-in. Subjects with 5 or more IDH events during this 8-week interval will be excluded.

The table below provides the corresponding Expected IDH Rate based on the Historical IDH Rate and summarizes the rules for escalation, de-escalation, or discontinuation based on the number of occurrences of IDH.

Historical IDH Rate over 8 weeks	Expected IDH Rate over 4 weeks	Escalation Rule	De-escalation or Discontinuation Rule
0	0	1 or less	2 in 4 weeks
1	1	2 or less	3 in 4 weeks
2	1		
3	2	3 or less	4 in 4 weeks
4	2		

Escalation Rules: A subject may be escalated to the next larger column size if they experience no more than 1 IDH event above their Expected IDH Rate in a 4-week treatment period and has an Hgb level \geq 9 g/dL.

De-escalation Rules: A subject should be de-escalated to a previously tolerated column size if at any time during a 4-week treatment period they experience 2 or more IDH events above the Expected IDH Rate and/or has a Hgb level $<$ 9 g/dL despite optimized ESA treatment.

Discontinuation Rules: A subject should be discontinued if they experience 2 or more IDH events above their Expected IDH Rate in a 4-week treatment period after de-escalation to the lowest column size (AKST1210 S-15) and/or has an Hgb level $<$ 9 g/dL despite optimized ESA treatment after de-escalation to the lowest column size (AKST1210 S-15). Subjects may also be discontinued at any time at the discretion of the investigator.

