As a reminder, all occurrences of IDH after the time of consent should be recorded as AEs. Refer to [Section 8](#) for additional information concerning safety reporting.

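### SAP 5.7.3 compares an 8-week chart count of IDH with 4-week on-study counts, with no time base and no period-matched control, so the change by column size is not a clean column effect

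*SAP*

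**What the plan says.** **The endpoint.** Protocol 4.2.2 and SAP 3.2 list the change in IDH rate above each subject's Historical rate, by column size, as a secondary endpoint. SAP 5.7.3 implements it as counts and percentages of subjects in three rows: Historical rate (0 to 4), number of IDH (0 to 6) and "Change in IDH Rate above the Historical IDH Rate (0,1,2, 3". The columns are S-15, S-25, S-35, overall AKST1210 and control. There is no formula and no time base.

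**The reference.** Protocol Appendix 17.1 defines the Historical rate as "The number of occurrences of IDH as documented in a subject's medical record during a recent, consecutive 8-week interval prior to randomization". It adds: "This 8-week period may include the 2-week Run-in". Subjects with 5 or more events in the window are excluded. So are those with 3 or more events in Run-in (Protocol 5.2).

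**The on-study count.** Protocol 7.1.1.2.2 states: "Seated/reclined BP will be recorded before each dialysis session, every 30 minutes during dialysis, and at the end of the session". It also says "Vital signs monitoring will occur at every visit", so the schedule covers Run-in as well as treatment. Subjects are actively monitored for IDH, and Appendix 17.1 requires that "all occurrences of IDH after the time of consent should be recorded as AEs". From Run-in onward, dialysis runs at no more than 250 mL/min for about 4 hours (Protocol 4.1).

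**A conversion exists, for another purpose.** Appendix 17.1 turns the Historical count into an Expected IDH Rate, "The expected number of occurrences of IDH per 4-week treatment period used to assess escalation, de-escalation, and discontinuation". SAP 5.7.3 does not refer to it.

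**The concern.** The two counts differ in source (routine chart against study procedures), in length (8 weeks against 4) and, for most or all of the reference window, in dialysis prescription. The reference is also selected to be low at entry. A change formed from them mixes any column effect with all four differences.

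The endpoint is meant to be read by column size. In the planned sequence, S-15, S-25 and S-35 belong to treatment periods 1, 2 and 3, yet control is one column with no breakdown by period. A reader therefore sees three within-arm changes and no like-for-like comparator for any of them. At stake is the description of one of the device's two tracked risks (IDH and anemia) by column size, which later studies would draw on.

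**Working it through.** **1. The plan's own figures.** With H the Historical count, Expected = H/2 rounded up. For H = 0, 1, 2, 3, 4 this gives 0, 1, 1, 2, 2. Expected + 1 gives the escalation limits 1, 2, 2, 3, 3, and Expected + 2 gives the de-escalation limits 2, 3, 3, 4, 4. All five rows of the Appendix 17.1 table are reproduced. The Protocol therefore handles the 8-to-4-week conversion for its rules, but SAP 5.7.3 does not carry it over.

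**2. How much of the reference window shares study methods.**
- Half-hourly BP: 0 to 2 of 8 weeks, so 0% to 25%, depending on whether Run-in is counted.
- AE recording: it starts at consent, and Protocol 4.1 places consent in Screening ("During Screening (Visit 1, Day -42 through Day -14"). If the window runs up to randomization, 2 to 6 of its 8 weeks fall after consent.

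**3. Expected change with no device effect.** Assumptions, not in the documents: Poisson counts; a true rate of 2 events per 8 weeks, hence 1.00 per 4-week period; charts capture a fraction f; Run-in is outside the window. H is Poisson with mean 2f, cut off above 4 by eligibility.

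At f = 100%: E[H] = (2 + 4 + 4 + 2.667)/(1 + 2 + 2 + 1.333 + 0.667) = 12.667/7 = 1.81.

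| Chart capture f | E[H], 8 weeks | 4-week base: 1.00 − E[H]/2 | Raw: 1.00 − E[H] |
|---|---|---|---|
| 100% | 1.81 | +0.10 | −0.81 |
| 75% | 1.43 | +0.29 | −0.43 |
| 50% | 0.98 | +0.51 | about 0 |
| 25% | 0.50 | +0.75 | +0.50 |

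If the overall AKST1210 and control columns use 12-week counts, the raw change at f = 100% is 3 × 1.00 − 1.81 = +1.19. The same subjects can thus show −0.81, +0.10 or +1.19 with no device effect and perfect charting.

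**4. Other rates, equal detection.** At 1 event per 8 weeks the change is +0.01 (common base) or −0.48 (raw). At 3 it is +0.31 or −0.88. Letting rates vary between subjects (gamma, mean 2, shape 1 or 2) gives +0.12 or +0.13 on the common base and −0.50 or −0.60 raw, so the signs are unchanged.

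**5. Whether Run-in is counted.** At rate 2, the ratio of on-study to Historical rate on a common base, for f = 100/75/50/25%, is 1.10/1.40/2.04/4.01 with Run-in outside the window and 1.11/1.33/1.68/2.40 with it inside. Where charts under-record, two identical subjects differ only because of this choice.

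**6. When the raw change turns positive.** Let k be study detection divided by chart detection, and w the weeks of the window already at study-level detection. Ignoring truncation, break-even is k/2 = [(8 − w) + kw]/8, so k = (8 − w)/(4 − w). That is k = 2 for w = 0 and k = 3 for w = 2; it is never reached for w = 6.

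**7. Fit of the categories.** With H from 0 to 4 and IDH from 0 to 6, a raw difference runs from 0 − 4 = −4 to 6 − 0 = +6, but the row offers only 0 to 3. At rate 2 with equal detection, 58% of subjects would have a negative raw change. On an unrounded 4-week base, odd H gives half-events, which have no category either.

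**8. Between arms.** Both arms share the reference definition, entry limits, BP schedule and AE recording. With no device effect, both expectations are equal at any f, so the AKST1210 minus control difference is 0 in expectation.

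**9. Precision of that difference.** Assuming 10 per arm and 1 event per 4 weeks in each arm: SE = √(1/10 + 1/10) = 0.447, and the 95% half-width is 1.96 × 0.447 = 0.88 event per period. Over 12 sessions that is 0.073 per session, against an assumed rate of 1/12 = 0.083. Extra variation between subjects would widen it.

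**The case against.** The strongest reply is that control is already in the table, under the same monitoring, that Protocol 10.4.1 promises between-group differences for secondary endpoints, and that SAP 5.7 calls the efficacy analyses descriptive. This largely stands: the randomized comparison is not biased in expectation. What is missing is control by period and an explicit difference with an interval.

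Four stronger readings are tempting, and the documents do not support them.
- *The change must rise on treatment even with an inert device.* This holds only on a common time base. A raw subtraction is negative or about nil in three of the four capture scenarios above. The documents do not say how often BP was taken or IDH charted in usual care, and IDH needs symptoms as well as a pressure fall, so extra readings alone do not create events.
- *At most a quarter of the window has study ascertainment.* That is true of half-hourly BP only; AE recording can reach back to consent.
- *The new dialysis prescription raises IDH.* The documents give neither direction nor size.
- *This table drives column-size decisions.* Those follow the Appendix 17.1 thresholds.

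It is also fair to say that the change above Historical is the Protocol's own endpoint, so it should be supplemented, not replaced.

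**Conclusion.** The point holds in a limited form. As specified, the within-arm change above Historical is not a clean column effect. With no device effect, its direction depends on a time base that the SAP leaves unstated. At 2 events per 8 weeks and equal detection, the change is about +0.1 event per 4 weeks on a common base, from entry truncation alone, and about −0.8 as a raw subtraction. Chart under-recording would add to either figure by an amount the documents do not give. These sizes rest on Poisson counts and the assumed rate and capture; the difference in source, window length and selection rests on the text.

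The randomized contrast escapes this bias in expectation, so the defect lies in the single-arm, by-column-size reading. It is worth correcting because the data needed are already collected.

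**What to change.** In SAP 5.7.3:
- Keep the Protocol endpoint as a descriptive row. State its formula and put both terms on one base (events per session or per 4 weeks). Add a category for decreases and make sure the categories cover the possible range.
- Show control by the same treatment period as each column size.
- Add the AKST1210 minus control difference in IDH per session within each treatment period, with a 95% CI, and name it as the comparison used to interpret the endpoint.
- Add Run-in IDH per session as a reference with the same monitoring and prescription and no device. Note that it is only 6 sessions and is truncated at fewer than 3 events.
- Flag for each subject whether the Historical window included Run-in.
- State that a within-arm change above Historical is not by itself evidence of a column effect.

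The cost is SAP wording and one reprogrammed table; no new data and no change to any clinical rule. The downsides are a noisy Run-in reference and wide intervals at about 10 per arm.

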5.7.4 Incidence of IDH Leading to De-escalation or Discontinuation

The number and percentage of subjects with any IDH leading to de-escalation or discontinuation from AKST1210/control will be summarized by treatment group and Total.

5.7.5 Incidence of Worsening Anemia by Column Size

The number and percentage of subjects with any worsening anemia will be summarized by column size (AKST1210 S-15, S-25, and S-35), overall AKST1210 and control. Worsening anemia is defined as subjects with a Hgb < 9 g/dL, which decreased from baseline (or the prior measurement) of no less than 1 g/dL.

5.7.6 Incidence of Anemia Leading to De-escalation or Discontinuation

The number and percentage of subjects with any anemia leading to de-escalation or discontinuation from AKST1210/control will be summarized by treatment group and Total.

5.7.7 Change from Baseline in Levels of b2M, Evaluation of Change Based on Column Size

Blood sampling for b2M concentration will occur at Run-in, during the treatment period, and at EOS. During the treatment period, blood samples will be collected at 3 sample locations (A, B, C, [Figure 2](#)) and at multiple time points prior to dialysis (PTD), at 1 hour, 2 hours, and at the end of dialysis (EOD) at the end of each 4-week treatment (V2.11, V3.11 and V4.11). Detailed collection schedule could be found in [Figure 2](#) and [Table 1](#).

[figure not shown]

Figure 2. The b2M sample locations in the control and the AKST1210 group.

Table 1. Collection schedule of b2M samples

| Study period | Run-in | Treatment period | | | | | | | | | | End of study | |
|-----------------|--------|----------------------|--------|---------|-----|----------------------|--------|---------|-----|----------------------|--------|--------------|---------------|
| Study visit | V1.5 | V2.11 | | | | V3.11 | | | | V4.11 | | | V6 |
| Study week(day) | | Week 4 (D4) | | | | Week 8 (D52) | | | | Week 12 (D80) | | | Week 14 (D96) |
| Column size | | 150 mL column (S-15) | | | | 250 mL column (S-25) | | | | 350 mL column (S-35) | | | |
| Timepoint | PTD | PTD | 1 hour | 2 hours | EOD | PTD | 1 hour | 2 hours | EOD | PTD | 1 hour | 2 hours | PTD |
| Sample location | A | A | A,B,C | A,B,C | A | A | A,B,C | A,B,C | A | A | A,B,C | A,B,C | A |

PTD: prior to dialysis; EOD: end of dialysis. Sample location A is before the AKST1210 column. Sample location B is after the AKST1210 column and before the hemodialyzer. Sample location C is after both the AKST1210 column and the hemodialyzer. In the control group, because there is no AKST1210 column, sample location A is the same as sample location B ([Figure 2](#)).

Three hypotheses will be tested to evaluate the effects of AKST1210 columns on b2M removal, including overall removal after AKST1210 treatment and instantaneous removal during AKST1210 treatment.

The first hypothesis is that active treatment with AKST1210 columns will change b2M levels significantly compared to the b2M changes in the placebo group. The changed b2M levels will be calculated as b2M levels from samples collected at sample location A prior to dialysis at V2.11, V3.11, V4.11, and V6 (EOS), minus the b2M levels at baseline (V1.5) at sample location A, respectively.

The second hypothesis is that the treatment duration (and/or column size) will significantly affect the b2M removal from baseline. The same changed b2M levels as in the first hypothesis will be used.

The third hypothesis is that the sizes of the columns will significantly affect the instantaneous clearance of b2M. The instantaneous clearance of b2M will be evaluated by 3 ratios in logarithmic scale: 1) B/A ratio at the active group, which is the instantaneous b2M removal ratio of AKST1210 (b2M levels at location B/ b2M levels at location A after 1 hour and after 2 hours, respectively); 2) C/A ratio at the active group, which is the instantaneous b2M removal ratio of AKST1210 and the hemodialyzer (b2M levels at location C/ b2M levels at location A after 1 hour and after 2 hours, respectively); and 3) C/B ratio at both treatment groups (C/A ratio in the control group), which is the instantaneous b2M removal ratio of the hemodialyzer (b2M levels at location C/ b2M levels at location B after 1hour and after 2 hours, respectively). The B/A ratio is solely for the effect of AKST1210 column sizes. The C/A ratio is for the combined effect of AKST1210 columns and hemodialyzer. And the C/B ratio (or the C/A ratio in the control group) is for the effect of hemodialyzer. The B/A ratio and C/A ratio will be analyzed to test the effects of column size on the instantaneous clearance of b2M. The analysis of C/B ratio (or the C/A ratio in the control group) will be only descriptive summary.

For the first hypothesis, the null and alternative are:

$$H_0: \mu_1C = \mu_1T \text{ vs. } H_A: \mu_1C \neq \mu_1T.$$

The null hypothesis states that there is no difference in mean change (μ_1) from baseline b2M levels as measured by the b2M levels at sample location A prior to dialysis between the control (C) and treated (T) groups after each of 4-week treatment and after the whole treatment period. The alternative hypothesis states that there is a difference in mean change from baseline b2M levels between the control and treated groups.

A mixed-effect model for repeated measures (MMRM) will be employed to analyze the change from baseline b2M levels at V2.11, V3.11, V4.11 and V6. The model will include the fixed effects of treatment (reference=control group),

baseline b2M levels, visit (as a categorical variable), treatment by visit interaction, and the random effect of intercept and dialyzer types (or sites, if ≥ 5 subjects per site). Depending on the data, compound symmetry, heterogeneous compound symmetry, an unstructured covariance structure will be used to model the within subject error. Least-square (LS) means, standard error (SE), and 95% confidence interval (CI) of the LS means will be provided for each treatment arm at each visit. P-values testing whether the LS means at each visit is significantly different from 0 will be provided, which indicates the significance of AKST1210 treatment on b2M removal from baseline within group over time. The difference in LS means between treatment arms and 95% CI of the difference will also be calculated. P-value for testing whether the difference is equal to zero at all these 4 visits will be provided and compared against the alpha significance level of 0.1, which indicate significance of AKST1210 treatment on b2M removal compared to the control group.

For the second hypothesis, the null and alternative are:

$$H_0: \mu_{2C} = \mu_{2T} \text{ vs. } H_A: \mu_{2C} \neq \mu_{2T}.$$

The null hypothesis states that there is no difference in mean change (μ_2) from baseline b2M levels as measured by the changed b2M levels at sample location A prior to dialysis at V2.11, V3.11 and V4.11 in the active group. The alternative hypothesis states that there is a difference in mean change from baseline b2M levels at least in one between-visits comparison.

The same MMRM will be used. But additional LS means of three between-visit comparisons in the active group, standard error (SE), and 95% CI of the LS means will be calculated. P-value for testing whether the difference is equal to zero at all three between-visit comparisons at the active group will be provided and compared against the alpha significance level of 0.1, which indicate the significance of different AKST1210 treatment durations (and/or column sizes) on b2M removal.

For the third hypothesis, the null and alternative are:

$$H_0: \mu_{iC} = \mu_{iT} \text{ vs. } H_A: \mu_{iC} \neq \mu_{iT}.$$

The null hypothesis states that there is no difference in mean instantaneous ratios (μ_i) as measured by B/A ratio and C/A ratio in the logarithmic scale among three AKST1210 columns, alone or combined with hemodialyzer, respectively. The alternative hypothesis states that there is a difference in instantaneous ratio among the three AKST1210 columns.

A mixed-effect models for repeated measures (MMRM) will be employed in the active group to analyze the instantaneous ratios of B/A ratio and C/A ratio. The

model will include the fixed effects of b2M levels at sample location A, column size (as categorical variable), hours (reference=1 hour), ratio types (B/A ratio or C/A ratio), column size by hours interaction, column size by ratio types interaction, hours by ratio types interaction, and three-way interaction of column size, hours and ratio types, as well as the random effects of intercept and dialyzer types (or sites). Depending on the data, compound symmetry, heterogeneous compound symmetry, an unstructured covariance structure will be used to model the within subject error. Least-square (LS) means, standard error (SE), and 95% CI of the LS mean will be provided for each AKST1210 column at each hour. The pairwise difference in LS means among three AKST1210 column size at 1 hour and 2 hours for both ratio types, and 95% CI of the difference will also be calculated. P-value for testing whether the difference is equal to zero will be provided and compared against the alpha significance level of 0.1, which indicates the significance of different AKST1210 column sizes on instantaneous b2M removal.

For the C/B ratio (or the C/A ratio in the control group), summary statistics will be provided for the active group and the control group at 3 visits.

Model diagnostics including residual and noniterative influence analysis will be conducted to ensure the MMRM assumptions (e.g. residual normality, and homogeneity of variance) and to identify potential outliers and influential observations. If residuals are not normal, logarithmic transformation will be applied to raw b2M levels before MMRM. No multiple comparison corrections will be performed as the aim of this study is to find trends in secondary endpoints instead of confirmation.

Sensitivity Analyses

The main analyses with the above MMRMs will use all available data. To check the robustness of the results, the following sensitivity analyses will be performed:

- The same MMRM models will be utilized for data from the PP subjects.
- For the first and the second hypotheses, the same MMRM models will be utilized, but focused on data at V2.11, V3.11 and V4.11 (removing V6).
- For the second hypothesis, a new MMRM model using the data from only the active group will also be performed with the fixed factors of baseline b2M levels and visits (V2.11, V3.11 and V4.11), and random effects of intercept and dialyzer types (or sites).

